4.2 EXCLUSION CRITERIA

Subjects who meet any of the following criteria will be excluded from participation in the study:

- 1. Female subjects who are pregnant, lactating, or planning to become pregnant during the study
- 2. Subjects with a current diagnosis of uncontrolled sleep apnea, as defined by their physician
- 3. Subjects with renal insufficiency, as defined by requiring dialysis or an estimated creatinine clearance of <30 mL/min, as calculated by the Cockcroft-Gault equation (see Appendix F)
- 4. Subjects with liver dysfunction defined as elevated liver function tests (alanine aminotransferase or aspartate aminotransferase) ≥3 times the upper limit of normal at Screening, or subjects with Child-Pugh Class B or C hepatic disease (see Appendix F)
- 5. Subjects with anemia, as defined by Screening hemoglobin < 9 g/dL
- 6. Subjects with an active infection or condition that would interfere with interpretation of study assessments
- 7. Subjects with a history of ischemic heart disease (defined as subjects who require antianginal therapy within 6 months of Screening or who have experienced a documented myocardial infarction within 6 months of Screening), or a history of left-sided myocardial dysfunction, as evidenced by a PAWP >15 mmHg or left ventricular ejection fraction <50%

- 8. Subjects with uncontrolled systemic hypertension, as evidenced by systolic blood pressure >160 mmHg or diastolic blood pressure >100 mmHg at Baseline
- 9. Subjects with severe hypotension, as evidenced by systolic blood pressure <90 mmHg or diastolic blood pressure <50 mmHg at Baseline
- 10. If a lung assessment has been completed as per standard of care, any subject with 1 or more of the following signs of documented relevant lung disease within 180 days of Baseline: total lung capacity <60% of predicted, or forced expiratory volume in 1 second <55% of predicted normal

- 11. Subjects with chronic musculoskeletal disorder or any other disease that would limit ambulation, or who are connected to a machine that is not portable
- 12. Subjects with a history of alcohol abuse or illicit drug abuse within 12 months of Baseline which, in the Investigator's opinion, would make the subject inappropriate for enrollment in a clinical study
- 13. Subjects with any other concomitant disease with life expectancy of <12 months from Baseline
- 14. Subjects with an unstable psychiatric condition or those not capable of understanding the objectives, nature, or consequences of the study, or who have any condition which, in the Investigator's opinion, would constitute an unacceptable risk to the subject's safety

- 15. Subjects who are currently receiving an investigational drug, have an investigational device in place, or who have participated in an investigational drug or device study within 180 days prior to Baseline. Participation in an observational study within 180 days prior to Baseline does not disqualify a subject from enrolling.
- 16. Subjects who have received a prostacyclin-class therapy within 28 days of Baseline.
- 17. Subjects who have a Registry to Evaluate Early and Long-Term PAH Disease Management (REVEAL) 2.0 Risk Score of 10 or greater (see Appendix J).

4.3 PRESCRIBED THERAPY

4.3.1 Concomitant Medications

Subjects are eligible for this study if they are either not receiving PAH-targeted therapy or are currently being treated with 1 or 2 FDA-approved oral PAH therapies consisting of an ERA and/or either a PDE5-I or an sGC for ≥45 days. They must be receiving a stable dose for ≥30 days prior to the Baseline Visit. If an FDA-approved treatment for PAH (other than study drug or a prostanoid used in vasoreactivity testing) is added during the study, the subject must be withdrawn from the study.

Subjects should be on stable doses of other medical therapies for at least 10 days prior to Baseline Visit with no dose adjustments, additions, or discontinuations. Exceptions to this are discontinuation or dose changes of anticoagulants and/or diuretics. Medications are also allowed to be temporarily discontinued if necessary for the safety of study-related medical procedures, such as RHC during Screening. Subjects should not have experienced recent changes to non-pharmacologic interventions, such as exercise, diet plans, pulmonary rehabilitation, sleep apnea treatment, etc., for at least 10 days prior to Baseline.

Any concomitant medications taken by the subject during the study should be recorded in the subject's source documents and transcribed to the subject's eCRF.

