3.3.2 Safety

3.3.2.1 Adverse Events and the AE Bothersome Survey

Adverse events will be captured from when the subject signs the informed consent form (ICF) until the subject completes the study or is withdrawn from the study. Adverse events should be followed until either resolution (or return to normal or Baseline values), until they are judged by the Investigator to no longer be clinically significant, or for at least 4 weeks if the AE extends beyond the final study visit (Week 16). All serious adverse events (SAEs) that occur during the study will be followed until resolution, death, or the subject is lost to follow-up, even if they are ongoing more than 4 weeks after completion of the final study visit.

The Investigator will administer the AE Bothersome Survey (Appendix E) at time points listed in Table 3-1 to collect information about prostanoid-related effects experienced by the subject. This questionnaire may be used to guide AE assessment and conversations about AEs that a subject is experiencing.

Events related to prostanoid therapy captured by the AE Bothersome Survey (Appendix E) should only be recorded as an AE and should only be captured as an SAE if the event is unusual with respect to intensity, frequency, or duration as compared with symptoms in the subject's medical history.

Events attributable to the progression of the disease under study (listed in Table 9-1) and events attributable to PAH symptomatology captured by PAH Symptom Score (Section

3.3.1.2) should only be recorded as an AE if the event is unusual with respect to intensity, frequency, or duration as compared with symptoms in the subject's medical history, or if there is a reasonable possibility that the event was caused by the study drug

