3.6 ESTIMATED STUDY DURATION

The per-subject study period is defined as the date the subject signs the ICF until the Week 16 Visit, the date the subject withdraws from the study, the date a subject dies, or the date a subject is lost to follow-up, whichever occurs first. Subjects who withdraw from study drug prior to Week 16 will be asked to remain in the study up to Week 16 and complete study assessments off treatment.

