8 STUDY TERMINATION

8.1 CRITERIA FOR SUBJECT WITHDRAWAL

A subject may voluntarily withdraw or be withdrawn from the study and/or study drug by the Investigator at any time for reasons including, but not limited to, the following:

- The subject wishes to withdraw from further participation.
- A serious or life-threatening AE occurs or the Investigator considers that it is necessary to discontinue study drug to protect the safety of the subject.
- The subject deviated from the protocol.
- The subject's behavior is likely to undermine the validity of his/her results.

If a subject is discontinued from the study prematurely, the Investigator must provide an explanation in the eCRF (Investigator's Comment Log) and complete the End of Study Record for that subject. If study drug has been administered, the Investigator should make every effort to perform all scheduled evaluations prior to discharge. In the event that a subject discontinues study drug prematurely due to an AE, the subject will be followed until either the Investigator determines that the AE has resolved, it is no longer considered clinically significant, the subject is lost to further follow-up, or for 4 weeks if the AE extends beyond the final visit.

If a subject discontinues study drug prior to completing the Week 16 Visit assessments, the Investigator will record the reason for withdrawal (eg, type of AE, lack of response), the dosing titration schedule (date and dose of last titration, date and last dose taken before study drug discontinuation), and if transitioning to a different pulmonary hypertension therapy, the pulmonary hypertension drug to which the subject is transitioning.

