9.2 DOCUMENTATION OF ADVERSE EVENTS

An AE or SAE occurring during the study must be documented in the subject's source documents and on the appropriate eCRF page. Information relating to the AE, such as onset and cessation dates and times, intensity, seriousness, relationship to the study drug, and outcome, is to be documented in the eCRF (see Appendix C). If several signs or symptoms are clearly related to a medically defined diagnosis or syndrome, the diagnosis or syndrome should be recorded on the eCRF page, not the individual signs and symptoms.

All AEs should be followed until either resolution (or return to normal or Baseline values), until they are judged by the Investigator to no longer be clinically significant, or for at least 4 weeks if the AE extends beyond the final visit. All SAEs that occur during the study will be followed until resolution, death, or the subject is lot to follow-up, even if they are ongoing more than 4 weeks after completion of the final visit. Supplemental measurements and/or evaluations may be necessary to investigate fully the nature and/or causality of an AE or SAE. This may include additional laboratory tests, diagnostic procedures, or consultation with other healthcare professionals. The eCRF pages should be updated with new or additional information.

The AEs reported by the subjects will be summarized by United Therapeutics Corporation during the study at intervals aligned with periodic safety update reports and at the end of the study.

For any nonserious AE that is outside the scope of the prostanoid AEs (headache, diarrhea, nausea, flushing, jaw pain, extremity pain, and vomiting) that subjects will be reporting during this study, the Investigator will be instructed to report the AEs in compliance with the FDA reporting responsibilities (MedWatch/spontaneous).

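### Adding another PAH drug forces withdrawal from the study, and AE capture ends at withdrawal, so new-onset events after that date are not collected; the rule also conflicts with the request that subjects off study drug stay to Week 16

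*Protocol*

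**What the plan says.** Five passages bear on the point.

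- **Protocol 4.3.1.** If an FDA-approved PAH treatment other than study drug, or a prostanoid used for vasoreactivity testing, "is added during the study, the subject must be withdrawn from the study". Protocol 8.1 distinguishes leaving the study from stopping study drug, so this wording means the study.
- **Protocol 3.3.2.1, repeated in SAP 3.7.1.** AEs are captured from consent "until the subject completes the study or is withdrawn from the study".
- **Protocol 3.6.** The per-subject period runs "until the Week 16 Visit, the date the subject withdraws from the study", or to death or loss to follow-up if earlier. The same section adds: "Subjects who withdraw from study drug prior to Week 16 will be asked to remain in the study up to Week 16", with assessments made off treatment.
- **Protocol 8.1.** For a subject who stops study drug early, the site records, "if transitioning to a different pulmonary hypertension therapy, the pulmonary hypertension drug to which the subject is transitioning". It does not say that such a subject leaves the study.
- **Protocol 3.3.2.1 and 9.2, on events already open.** "All serious adverse events (SAEs) that occur during the study will be followed until resolution, death, or the subject is lost to follow-up". Other AEs are followed until resolved or judged no longer clinically significant, or "for at least 4 weeks if the AE extends beyond the final visit".

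**The concern.** The plan keeps a subject who stops study drug and takes nothing else under observation to Week 16, yet ends observation of a subject who is given another PAH drug. The second subject is plausibly the sicker one. Significant signs or symptoms of PAH are one of the two reasons the protocol gives for refusing, stopping or reversing transition (6.1, 7.3.4), and adding PAH therapy is a natural response to worsening. If follow-up stops for a reason linked to the risk of further events, the AE, SAE and death tables will tend to understate that risk.

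Safety conclusions here rest largely on AE data. SAP 3.7.2 neither lists nor summarizes vital signs and laboratory tests. There is no control arm in which the same loss would show. SAP 4.1 compares the interim safety profile with historical transition data, and truncated follow-up weakens that comparison.

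**Working it through.** The documents state no rate of added PAH therapy and no calculated sample size, so there is no plan figure to reproduce. The check is mainly textual.

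**Step 1: apply the rules to each kind of subject.**

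| Subject | Text that applies | Capture of new events |
|---|---|---|
| Stops study drug, no other PAH drug | 3.6 | Continues to Week 16 if the subject agrees to stay |
| Transition refused or reversed, treated with Remodulin | 6.1 and 7.3.4; 4.3.1 exempts study drug | Continues to Week 16 |
| Stops study drug, starts another PAH drug | 3.6 keeps the subject, 4.3.1 removes the subject, 8.1 foresees the switch | Conflict; under 4.3.1 it ends at withdrawal |
| Adds another PAH drug while on study drug | 4.3.1; 3.6 does not address this case | Ends at withdrawal |

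The gap occurs in the last two rows. The contradiction with 3.6 occurs only in the third.

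**Step 2: what is and is not lost after withdrawal.**

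- Kept: SAEs with onset before withdrawal, including a death that follows from one. AEs still open are followed as described above. AEs are also recorded at the Early Study Withdrawal visit (7.3.7).
- Not collected: AEs and SAEs with onset after withdrawal, and deaths not arising from a recorded SAE. I found no passage that sets a later window for new events or vital status. Section 9.3 requires SAE reporting within 24 hours of awareness but requires no contact after withdrawal.
- The safeguard is incomplete. Under 3.3.2.1, events of disease progression are recorded as AEs only if unusual for that subject or possibly caused by study drug. The worsening behind the added drug may therefore not be an open AE at withdrawal.

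**Step 3: follow-up removed per subject.** Day 1 to Day 113 is 113 − 1 = 112 days. Days removed = 113 − day of withdrawal.

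- Day 29: 113 − 29 = 84; 84/112 = 75%
- Day 57: 113 − 57 = 56; 56/112 = 50%
- Day 85: 113 − 85 = 28; 28/112 = 25%

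**Step 4: scale in the cohort (illustration).** The targets of about 30 (Protocol 10.2) and about 35 (SAP 2.2.3) are evaluable subjects, and the SAP defines these as completing Week 16. A withdrawn subject is in the Safety Population but not among the 35. If 35 complete and 2 to 5 more are withdrawn under 4.3.1 (an assumption), the share with truncated follow-up is 2/37 = 5.4% to 5/40 = 12.5%. In a cohort of 30 to 35, one subject is 1/30 = 3.3 to 1/35 = 2.9 percentage points.

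If 1 to 5 subjects (k) are withdrawn and each has a 10% to 30% chance (p) of a new SAE or death before Week 16 (both assumed), the chance that at least one goes unseen is 1 − (1 − p)^k. That runs from 1 − 0.9 = 10% to 1 − 0.7^5 = 83%. The width of this range shows how little can be said about frequency.

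**The case against.** A reader might infer that all later SAEs and deaths are lost in the subjects who worsen. The documents do not support that, for two reasons. SAEs begun before withdrawal are followed to resolution, death or loss to follow-up. And worsening need not lead to 4.3.1: a subject whose transition is refused or reversed can be treated with Remodulin, has no dose ceiling, and keeps full AE capture. Both limits stand.

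It can also be said that 4.3.1 is a specific exception to a general request in 3.6, and that the replacement drug in 8.1 is exit data, equally consistent with leaving the study. That reading is possible, but neither section refers to the other and sites could apply them differently. It would also leave the gap in new-event capture untouched.

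A further objection is that the fault lies in the AE window, since withdrawal for deviation, nonadherence or pregnancy ends capture in the same way. This is fair, and the fix therefore has to reach 3.3.2.1 and SAP 3.7.1. The added-drug case still stands out because withdrawal is mandatory and the trigger is plausibly related to outcome.

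Finally, the analysis is descriptive, reasons for early discontinuation are tabulated (SAP 3.3.1), and later events would be confounded by the new drug. The tabulation shows that subjects left, not what happened to them. Confounding is a reason to flag the data, not to leave the events uncollected.

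**Conclusion.** The point holds in limited form. Followed exactly, the plan does not collect new-onset AEs and SAEs, or deaths unconnected to a recorded SAE, once a subject is withdrawn because a PAH drug was added. For a subject who stops study drug and switches, 4.3.1 and 3.6 give opposite instructions and must be reconciled.

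The loss is 25% to 75% of the 112-day period for withdrawal between Day 85 and Day 29. How many subjects are affected cannot be derived from the documents, and the Remodulin route may keep the number small. That the loss is informative is a reasonable inference, not something the documents show; it rests on added PAH therapy being a marker of worsening. It would go too far to conclude that the safety tables are materially biased. In a cohort of this size, though, one unseen event is about 3 percentage points, and preventing the loss is cheap.

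**What to change.** 1. Reconcile Protocol 4.3.1, and 4.3.2 on additions of PAH medication, with 3.6 and 8.1, so that the end of study treatment and the end of study follow-up are separate. Whether study drug continues after another PAH drug is added, and which treatment rule applies, is for the sponsor to settle.
2. In Protocol 3.3.2.1 and SAP 3.7.1, state that after a PAH drug is added, the drug and its start date are recorded and AEs, SAEs and vital status are collected to Day 113 unless the subject withdraws consent. The sponsor could consider the same sentence for other withdrawals in which consent is not withdrawn.
3. In the SAP, include these events in the Safety Population tables. Flag efficacy data obtained after the added drug so that summaries can be shown with and without them.

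The cost is a protocol amendment with the approvals that 13.1 requires, a SAP flag, and contacts and visits already on the schedule for a few subjects. Some Week 16 data will then be collected on another PAH drug, which is why the flag is needed.

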4.3.2 Other Treatments

During the study, adjustments, additions, or discontinuations of non-pharmacologic interventions, such as exercise, diet plans, pulmonary rehabilitation, sleep apnea treatment, medications approved for PAH, etc, should not occur. Adjustments, additions, or discontinuations of other concomitant medications for other non-PAH diseases can occur.

5 SUBJECT ENROLLMENT

Any subject who meets the inclusion and exclusion criteria will be eligible to enroll in this study. As this is an uncontrolled study, measures to minimize bias and procedures relating to randomization are not applicable.

5.1 TREATMENT ASSIGNMENT

During the study, subjects will be receiving Orenitram and Remodulin supplied by the Sponsor. Subjects who have completed the Week 16 Visit will be transitioned off clinical study material onto commercially available Orenitram or Remodulin, as clinically appropriate.

5.2 RANDOMIZATION

This study does not employ randomization.

5.3 BLINDING

This is an open-label study.

6 DRUGS AND DOSING (OR TREATMENT PROCEDURES)

6.1 DRUG DOSAGE, ADMINISTRATION AND SCHEDULE

Remodulin will be provided in vial strengths of 1 mg/mL, 2.5 mg/mL, 5 mg/mL, and 10 mg/mL. Following completion of Baseline assessments, Remodulin will be initiated at 2 ng/kg/min SC or IV in an inpatient or outpatient setting. IV Remodulin may be administered through an indwelling central venous catheter or a peripherally inserted catheter, as clinically indicated. At the request of the Investigator, nursing support will assist subjects with initiation of SC or IV Remodulin, pump use, Remodulin dispensing, Remodulin titration, and adverse event management. If necessary, subjects can switch from IV to SC Remodulin, or SC to IV Remodulin, at the discretion of the Investigator.

Up-titration of Remodulin will continue as tolerated. Subjects should be optimized on Remodulin therapy prior to transition to Orenitram; a dose should be achieved that improves the symptoms of PAH while minimizing excessive pharmacologic effects of Remodulin. There is no maximum Remodulin dose during the study.

Subjects may transition at Weeks 2, 4, or 8 if they have achieved a minimum Remodulin dose of 20 ng/kg/min and the Investigator deems the subject suitable for transition. Subjects will transition from Remodulin to Orenitram over the course of 1 to 21 days in an inpatient or outpatient setting using a cross-taper method (ie, decreases in Remodulin dose coincide with increases in Orenitram dose). Orenitram will be provided in the extended-release tablet strengths of 0.125 mg, 0.25 mg, 1 mg, 2.5 mg, and 5 mg. Subjects will be instructed to take the appropriate number of 0.125 mg, 0.25 mg, 1 mg, 2.5 mg, and 5 mg tablets based upon their Remodulin dose and the transition schedule chosen by their healthcare provider.

Transition may be reversed or stopped if the Investigator feels it is necessary due to significant signs or symptoms of PAH or due to serious safety concerns. If the Investigator deems a subject unsuitable for transition to Orenitram due to significant signs or symptoms of PAH or any other serious safety concerns, the subject may remain on Remodulin for the duration of the study. However, the subject should be continually assessed to determine if they become stable enough for transition to Orenitram. All subjects still on Remodulin at Week 8 should transition to Orenitram regardless of their Remodulin dose unless the Investigator deems them unsuitable for transition to Orenitram due to significant signs and symptoms of PAH or any other serious safety concerns.

Following completion of transition, Orenitram dose titration will continue in the outpatient setting through Week 16 to reach the maximum tolerated dose by increasing the dose by 0.125 mg TID every 3 to 4 days as tolerated, with the goal of achieving a maximum tolerated dose by the end of Week 16. A slower titration rate may be used if the subject experiences adverse effects. There is no maximum Orenitram dose during the study.

Orenitram will be dosed TID with food. Dosing will take place approximately every 6 to 8 hours, with adjustments permitted based on the subject's lifestyle and schedule. Study subjects should take their study drug at approximately the same times each day. Tablets must be swallowed whole and not chewed, as this will result in inappropriate delivery of the active ingredient. If the tablet is inadvertently damaged during administration, the subject/caregiver should contact site personnel to be monitored for the onset of symptoms due to possible inappropriate drug release. Subjects must not "make-up" or "double-up" on missed doses of

Orenitram. If dosing is interrupted for longer than 24 hours, consideration should be given to gradually re-titrating the subject's dose to the last dose administered prior to the dose interruption, particularly in cases where the last dose prior to interruption was greater than 3 mg.

In the event of a planned short-term treatment interruption for subjects unable to take oral medications after beginning transition to Orenitram, consider a temporary infusion of SC or IV Remodulin using the following equation to calculate the dose of Remodulin:

Remodulin (ng/kg/min) =
$$(139 \times \text{Orenitram TDD [mg]}) \div \text{weight (kg)}$$

Subjects who complete the Week 16 Visit will be transitioned off clinical study material to commercially available Orenitram or Remodulin, as clinically appropriate, through their health and/or prescription insurance. For subjects who are uninsured or underinsured, the study site can help them apply for the United Therapeutics Patient Assistance Program (PAP). Through the PAP, subjects can receive a supply of Orenitram or Remodulin free of charge for a period of 1 year if eligible. After 1 year, subjects may apply for a renewal of PAP assistance on an annual basis. Subjects' eligibility to participate in this program is based on financial inability to pay for the drug, lack of insurance coverage, and other criteria which subjects can discuss with their study site.

